4.3 Definition of Withdrawal

The group of patients who withdrew in the Placebo-controlled Period before receiving any IMP in the Extension period will be described as *withdrawn* in the Placebo-controlled Period. The complementary group will be described as *completed* in the Placebo-controlled Period.

Similarly, for the Extension Period the group of patients who withdrew after receiving IMP in the Extension Period will be described as *withdrawn* in the Extension Period and the complementary group will be described as *completed* in the Extension Period.

4.4 Definition of Planned versus Actual Treatment

Every 12 weeks, patients will receive either eptinezumab 300 mg, eptinezumab 100 mg, or placebo in the Placebo-controlled Period and either eptinezumab 300 mg or eptinezumab 100 mg in the Extension Period.

Planned treatment is defined as the treatment a patient was randomized to.

Actual treatment is defined as the treatment a patient actually received during the study. If a patient received a different dose than what was planned at a given visit, the actual treatment in the relevant Period will equal the highest dose received. The actual treatment group will be determined separately for the Placebo-controlled Period and the Extension Period.

The term *treatment sequence* will be used to denote the treatment groups arising by combining the treatments received in the Placebo-controlled Period and the treatments received in the Extension Period, i.e. if all patients receive their treatment as planned the 4 groups are: Placebo-eptinezumab 100 mg, placebo-eptinezumab 300 mg, eptinezumab 100 mg, and eptinezumab 300 mg-eptinezumab 300 mg.

For reporting purposes, the following will be summarized by planned treatment:

- Efficacy
- Demographics and baseline characteristics
- Disposition
- eDiary compliance
- Concomitant medication

And the following will be summarized by actual treatment:

- Adverse events
- Exposure
- Disposition
- Laboratory parameters, vital signs, ECG, and C-SSRS

Unless otherwise specified, data listings will display actual treatment.

4.5 Definition of Migraine and Headache Days

For the purpose of endpoint derivations, the following definitions of migraine and headache days will be used. The definition of a migraine day reflects the strategy chosen to handle the intercurrent event of using acute migraine medication in the primary estimand, as outlined in Sections 12.3.1 and 12.3.3.

In this document, the term headache will encompass both headaches and migraine headaches. Migraine headaches (henceforth simply referred to as "migraines") are a subgroup of headaches with characteristics outlined below (Section 4.5.1). Using this definition, we have that all migraines are headaches but not all headaches are migraines.

Headaches will be self-reported by the patient using an electronic headache diary (eDiary). The eDiary is split into two parts, the headache diary and the evening diary. The headache diary is the part of the eDiary where the start and stop date and times of experienced headaches are recorded along with headache characteristics used for classifying headaches as migraines, and the evening diary is the part of the eDiary that patients are expected to complete each day during the study regardless of whether or not they experienced a headache on that day.

Randomization is stratified by Monthly Headache Days (MHDs) at baseline (≤ 14 MHDs/>14 MHDs). The stratum is based on a calculation performed directly in the eDiary at Baseline. The eDiary uses an algorithm described in the Project Design Specification (PDS), a document providing the technical specifications for the set-up of the eDiary, for determining whether a day in the screening period classifies as a day with a headache or a day with a migraine. Patients are deemed eligible if, according to this algorithm, they fall into the criteria for CM or EM as defined in inclusion criterion 10 in the *Clinical Study Protocol* (ed. 1.0 and 2.0), i.e:

- For patients with CM: Migraine occurring on ≥8 days and headache occurring on >14 days.
- For patients with EM: Migraine occurring on ≥4 days and headache occurring on ≤14 days

In this document, whenever stratum or stratification factor is mentioned, the reference is to this classification into EM and CM that was used for randomization.

The PDS definition of a migraine day can be seen in Appendix III.

4.5.1 Migraine Day

A migraine day is defined as any day with a headache that meets criteria A, B, C or D listed below:

A. All of the following criteria:

- 1. Lasted 4 hours or more
- 2. Had at least 2 of the following:
 - a. Unilateral location
 - b. Pulsating quality
 - c. Moderate or severe pain intensity
 - d. Aggravation by or causing avoidance of routine physical activity
- 3. Had at least 1 of the following:
 - a. Nausea
 - b. Vomiting
 - c. Photophobia and phonophobia
- B. A headache that lasted 30 minutes or more and patient had an aura with the headache
- C. A headache that lasted 30 minutes or more and met 2 of the 3 following criteria:
 - 1. Lasted 4 hours or more
 - 2. Had at least 2 of the following:
 - a. Unilateral location
 - b. Pulsating quality
 - c. Moderate or severe pain intensity
 - d. Aggravation by or causing avoidance of routine physical activity
 - 3. Had at least 1 of the following:
 - a. Nausea
 - b. Vomiting
 - c. Photophobia and phonophobia
- **D.** Patient took medication to treat the headache because they believed they were having a migraine

4.5.2 Headache Day

A headache day is defined as any day with a headache that meets one of the following criteria:

- Lasted 30 minutes or more
- Meets the criteria for being a migraine, i.e. fulfils either criteria A, B, C or D above (see Section 4.5.1)

5 Analysis Sets

The following analysis sets will be used to analyse and present the data:

- all-patients-randomized set (APRS) all randomized patients
- *all-patients-treated set* (APTS) all patients in the APRS who received at least one infusion of the double-blind IMP
- *full-analysis set* (FAS) all patients in the APTS who had a valid baseline assessment and at least one valid post-baseline 4-week assessment of MMDs in Weeks 1-12
- *all-patients-treated-long-term* set (APTS_LT) all patients in the APRS who received at least one infusion of IMP and had a visit in the Extension Period
- *full-analysis-long-term set* (FAS_LT) all patients in the APTS_LT who had a valid baseline assessment and a valid assessment of monthly migraine days in the Extension Period

The patients and data will be classified into the analysis sets according to these definitions at separate *Classification Meetings*:

- For the reporting of the Placebo-controlled Period, the Classification meeting will be held after the data base release for the reporting of the Placebo-controlled Period but before the blind has been broken and will concern the classification into APTS and FAS.
- For the *addendum to CSR*, the Classification meeting will be held after the data base release for the reporting of the Extension Period and will concern the classification into APTS_LT and FAS_LT.

Efficacy analyses of the Placebo-controlled Period will be based on FAS, and efficacy analyses in the Extension Period will be based on FAS_LT.

Safety tables (including exposure and concomitant medications) will be based on APTS in the Placebo-controlled Period and APTS_LT in the Extension Period.

6 Descriptive Statistics

Unless otherwise specified, summary statistics (n, arithmetic mean, standard deviation [SD], median, lower and upper quartiles, minimum and maximum values) will be presented for continuous variables, and counts and, if relevant, percentages will be presented for categorical variables.

Unless otherwise specified, data listings for the Placebo-controlled Period will include site, treatment group, patient screening number, sex, age, race, and baseline weight. For the Extension Period, the listings will include both treatment group in the Placebo-controlled Period and treatment group in the Extension Period in addition to the variables included in listings for the Placebo-controlled Period.

7 Patient Disposition

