12.1 General Efficacy Analysis Methodology

Unless otherwise specified, all the efficacy analyses for the Placebo-controlled Period will be based on the FAS and all the efficacy analyses for the Extension Period will be based on the FAS_LT.

All the tables and graphs will be presented by treatment group for the Placebo-controlled Period and both by treatment group and treatment sequence group for the Extension Period.

All the p-values will be based on two-sided tests; the confidence intervals (CIs) will be twosided; and the endpoints not included in the testing strategy will be presented with nominal pvalues and 95% CIs.

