- *Withdrawal due to lack of efficacy*: Will be addressed using a treatment policy strategy where the available values of HIT-6 are used regardless of patients withdrawing due to lack of efficacy
- *Withdrawal due to adverse event*: Will be addressed using a treatment policy strategy where the available values of HIT-6 are used regardless of patients withdrawing due to adverse events

Based on this, the key secondary estimand for evaluating the health-related quality of life and work productivity impact objective of the study will be the effect of eptinezumab on change from baseline in HIT-6 score regardless of patients withdrawing due to lack of efficacy or adverse events and regardless of use of acute or preventive migraine medication and infusion interruptions or terminations.

In addition, the following two attributes differ from the primary and other key secondary estimands:

- The endpoint to be obtained is the change from baseline in HIT-6 at Week 12
- The **population-level summary** is the least squares mean difference between eptinezumab and placebo for the endpoint

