12.4.2 Analysis of the Key Secondary Endpoints

50% and 75% response

The two key secondary endpoints, 50% response (Weeks 1-12) and 75% response (Weeks 1-12) will be analysed using logistic regression. The model will include baseline MMDs as a continuous covariate, and treatment and stratification factor (MHDs at baseline: $\leq 14 />14$) as factors. The SAS[®] code for these key secondary analyses is shown in Appendix IV.

The logistic regression model will be fitted using the maximum likelihood (ML) method and the logit link function.

The odds ratios for eptinezumab 300 mg and eptinezumab 100 mg compared to placebo will be estimated from the model and presented with p-values based on the likelihood ratio test and 95% CIs based on the profile likelihood.

The nominal p-values comparing each dose of eptinezumab to placebo will be presented. The comparisons will be part of the testing strategy described in Section 12.2.

In addition, the differences in response proportions between each dose of eptinezumab and placebo will be presented.

Change from Baseline in the number of MMDs (Weeks 13-24)

Changes from Baseline in MMDs at Weeks 1-4, Weeks 5-8, Weeks 9-12, Weeks 13-16, Weeks 17-20, and Weeks 21-24 will be analysed using the same methodology as described in Section 12.3.2 for the primary endpoint.

The mean differences between each dose of eptinezumab and placebo will be estimated based on the least squares means for the treatment-by-visit interaction in the MMRM model. The estimates will be presented with nominal p-values and 95% CIs. The comparisons will be the contrasts between each dose of eptinezumab and placebo averaged across Weeks 13-24. The comparisons will be part of the testing strategy described in Section 12.2.

Change from Baseline in HIT-6

Changes from Baseline in HIT-6 total score at weeks 4, 8, 12, 16, 20, and 24 will be analysed using the same methodology as described in Section 12.3.2 for the primary endpoint, replacing baseline MMD score with baseline HIT-6 score in the model.

The mean differences between each dose of eptinezumab and placebo will be estimated based on the least squares means for the treatment-by-visit interaction in the MMRM model. The estimates will be presented with nominal p-values and 95% CIs. The comparisons will be the contrasts between each dose of eptinezumab and placebo at Week 12. The comparisons will be part of the testing strategy described in Section 12.2.

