19.1.1.1 Monthly Migraine Days (MMDs)/Monthly Headache Days (MHDs)

The following describes the derivation of MMDs. The derivation of MHDs follows the same principles.

4-Week Intervals

For Baseline and each 4-week period post-baseline in the study, the number of MMDs will be derived as the number of migraine days within each 28-day interval using the imputation rules described below. The 4-week periods post-baseline that are considered are the following: Weeks 1-4, Weeks 5-8, Weeks 9-12, Weeks 13-16, Weeks 17-20, Weeks 21-24, Weeks 25-28, Weeks 29-32, Weeks 33-36, Weeks 37-40, Weeks 41-44, Weeks 45-48, Weeks 49-52, Weeks 53-56, Weeks 57-60, Weeks 61-64, Weeks 65-68, Weeks 69-72.

In general, for 4-week periods where the eDiary is completed on at least 14 days out of the 28 days, prorating will be used to calculate the MMDs, and for 4-week periods where the eDiary is completed on less than 14 days out of the 28 days, the MMDs will be set to missing. However, there are cases where weighting will be used when less than 14 days have been completed, and an overview is given in Panel 5.

Prorating

Intended to be used for 4-week periods where the eDiary is completed on at least 14 out of the 28 days, the prorating procedure consists of imputing days with missing information with the observed mean number of migraine days in the period as follows:

28*(Reported Migraine Days/Reported eDiary Days)

This imputation rule will also be used for the Baseline value regardless of the number of reported eDiary days in the screening period. Patients are, however, required to demonstrate compliance with the eDiary and fill it out for at least 24 out of the 28 days in the screening period in order to be eligible for randomization.

Weighting

Intended to be used in special cases for the first 4-week period post-baseline, where the eDiary is completed on less than 14 days out of the 28 days due to withdrawal. When weighting is used, the number of MMDs is derived as a weighted sum of the observed mean number of migraine days in the period and the mean MMDs for the preceding period as follows:

$$28*(W*X + (1 - W)*X_p),$$

where $W = Reported \ eDiary \ Days/13$, $X = Reported \ Migraine \ Days/Reported \ eDiary \ Days$, and $X_p = preceding \ MMDs/28$.

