Patients who withdraw due to lack of efficacy so early that they only have post-baseline data from Weeks 1-4 will have their MMDs calculated using weighting for Weeks 1-4 if they have less than 14 days of eDiary reporting during the first 4 weeks of the study. If they have 14 days or more in this period, their MMDs for Weeks 1-4 will be calculated using prorating.

Patients who withdraw due to adverse events so early that they only have post-baseline data from Weeks 1-4 will have their MMDs calculated using weighting for Weeks 1-4 if they have less than 14 days of eDiary reporting during the first 4 weeks of the study. If they have 14 days or more in this period, their MMDs for Weeks 1-4 will be calculated using prorating.

	Number of Reported eDiary Days		ed eDiary Days in Period
Description	4-Week Period	0-13	14-28
All patients randomized	Baseline	Prorating*	Prorating
Patients not withdrawing due to lack of efficacy/adverse event	Weeks 1-4	None (missing)	Prorating
Patients not withdrawing due to lack of efficacy/adverse event	4-week periods after week 4	None (missing)	Prorating
Patients withdrawing due to lack of efficacy	Weeks 1-4	Weighting	Prorating
Patients withdrawing due to lack of efficacy	4-week periods after week 4	None (missing)	Prorating
Patients withdrawing due to adverse event	Weeks 1-4	Weighting	Prorating
Patients withdrawing due to adverse event	4-week periods after week 4	None (missing)	Prorating

Panel 5 Overview of Imputation Rules for 4-Week Periods for eDiary Data

*Patients are required to complete the eDiary for at least 24 days during the first 28 days of screening to be eligible

In case of a reporting day where a patient answers in the evening diary that they experienced a headache on that day but then never fills out an actual headache in the headache diary, the day will be assigned as a no headache and no migraine day.

When the number of MMDs have been calculated for a given 4-week period, the result will be rounded to two decimals.

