19.2.1 Clinical Outcome Assessments (COAs) - Scales

For treated patients withdrawing prior to Week 24, the withdrawal visit scheduled 12 weeks after the last IMP infusion will also include efficacy evaluations (PGIC, MBS, HIT-6, MSQ, EQ-5D-5L, HCRU, and WPAI:M). These assessments will be assigned to either Visit 5 or Visit 8 according to when the patient was withdrawn as follows:

- For patients withdrawing prior to Visit 5, the assessments from the Withdrawal Visit will be assigned to nominal Visit 5
- For patients withdrawing after Visit 5 (but prior to Visit 8), the assessments from the Withdrawal Visit will be assigned to nominal Visit 8.

Unscheduled visits will not contain assessments of the COAs mentioned above. In relation to the nominal visits post-Baseline, a patient can complete their COAs 3 days before the visit. In case of duplicate scale assessments in relation to a nominal visit, i.e. if a patient fills out the scales 3 days before the visit and the visit is postponed afterwards implying that the patient has to complete the COA again, the latest assessment will be used.

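### HIT-6 and the other questionnaires are analysed in a set whose entry depends on diary completeness, so scores collected from treated patients with no valid diary month in Weeks 1-12 are left out

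*SAP*

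**What the plan says.** SAP Section 5 defines the FAS as "all patients in the APTS who had a valid baseline assessment and at least one valid post-baseline 4-week assessment of MMDs in Weeks 1-12". SAP Section 12.1 then states: "Unless otherwise specified, all the efficacy analyses for the Placebo-controlled Period will be based on the FAS". Protocol Section 16.2 has essentially the same FAS definition.

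For HIT-6, SAP Section 12.4.2 says "Changes from Baseline in HIT-6 total score at weeks 4, 8, 12, 16, 20, and 24 will be analysed using the same methodology" as the primary endpoint and names no set of its own. Neither does the placebo-based multiple imputation for HIT-6 (Section 12.4.4), nor the analyses of PGIC, MBS, MSQ, EQ-5D-5L and WPAI (Section 12.5).

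Whether a diary month is valid follows from SAP Section 19.1.1.1. The general rule is that "for 4-week periods where the eDiary is completed on less than 14 days out of the 28 days, the MMDs will be set to missing". The exception covers Weeks 1-4 for withdrawals due to lack of efficacy or an adverse event: "Patients who withdraw due to adverse events so early that they only have post-baseline data from Weeks 1-4 will have their MMDs calculated using weighting" when fewer than 14 days were reported, with a matching sentence for lack of efficacy.

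The HIT-6 estimand in Section 12.4.1 is the "effect of eptinezumab on change from baseline in HIT-6 score regardless of patients withdrawing due to lack of efficacy or adverse events". Withdrawal for other reasons is not among the differences listed for HIT-6, so the treatment-policy strategy of Section 12.3.3 carries over. Under Section 19.2.1, for patients withdrawing before Week 24, "the withdrawal visit scheduled 12 weeks after the last IMP infusion will also include efficacy evaluations". For those who leave before Visit 5, these scores are assigned to Visit 5, that is, Week 12.

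**The concern.** HIT-6 is completed on its own 4-weekly schedule, so whether a score exists does not depend on whether the diary was filled in. Making the HIT-6 analysis conditional on a valid diary month selects patients on post-randomisation behaviour in a different instrument.

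It also departs from the estimand. The population in SAP Section 12.3.1, which HIT-6 inherits, carries no diary condition, and treatment policy for other-reason withdrawals means that collected scores are used. For some patients the plan arranges to collect a Week 12 HIT-6 score at the Withdrawal Visit and then excludes them from the analysis. The HIT-6 sensitivity analysis names no wider set, so it does not bring them back. At stake are observed values for an endpoint in the confirmatory sequence for both doses.

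**Working it through.** **Who leaves the FAS although HIT-6 was collected.** Tracing Section 19.1.1.1 and Panel 5 into the FAS definition gives:

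- (a) Patients still in the study with fewer than 14 diary days in each of the three months. All three months are missing.
- (b) Other-reason withdrawals with no month of 14 or more diary days. Weighting does not apply to them. The protocol provides two routes. One is withdrawal for not complying with study procedures (Protocol 5.4; Protocol 9.2.2 asks for at least 85% diary compliance). The other is consent withdrawn by telephone with agreement to attend the Withdrawal Visit, where data up to that visit are used (Protocol 8.9) but diary entry is no longer expected (SAP Section 2).
- (c) Lack-of-efficacy or adverse-event withdrawals with zero diary days. Panel 5 assigns weighting to 0-13 days, but the formula is undefined at zero (below).
- (d) Possibly, lack-of-efficacy or adverse-event withdrawals with sparse data after Week 4. The text limits weighting to patients whose post-baseline data come only from Weeks 1-4; Panel 5 has no such limit.

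**Who stays.** The weighting formula is 28 × (W × X + (1 − W) × Xp), with W = diary days/13, X = migraine days/diary days and Xp = preceding MMDs/28. For an illustrative baseline of 14 MMDs (Xp = 0.5):

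- 1 diary day, 0 migraine days: 28 × (1/13 × 0 + 12/13 × 0.5) = 12.92
- 5 diary days, 3 migraine days: 28 × (5/13 × 0.6 + 8/13 × 0.5) = 15.08
- 0 diary days: X = 0/0, undefined

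So a single diary day keeps an early lack-of-efficacy or adverse-event withdrawal in the FAS.

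**The plan's own figure.** The only planning number tied to such exclusions is the 2% without a post-baseline primary assessment (Protocol 16.10, SAP Section 16). It reproduces within the stated power:

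- n = 280 × 0.98 ≈ 274 per arm
- Differences: 0.4 × 0.69 + 0.6 × 2.03 = 1.494 (100 mg); 0.4 × 1.11 + 0.6 × 2.60 = 2.004 (300 mg)
- SD = √(0.4 × 3.1² + 0.6 × 5.8²) = 4.902
- Two-sided 5% power: 94.6% and 99.8%, and by a 10,000-run simulation 94.3% and 99.8%, against the stated 94% and 99%

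**Size for HIT-6.**

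- Patients: 0.02 × 840 = 16.8, or 5.6 per arm. This is an upper figure under that assumption, since some of these patients will have no HIT-6 either.
- Standard error: √(280/274.4) = 1.010, about 1% larger.
- Range for an assumed 0.5% to 5% excluded: 4 to 42 patients, standard error 0.3% to 2.6% larger.
- Shift in the contrast if a share f is lost in one arm only and differs from the rest by D points: f × D. With f = 0.02 and D assumed 2 to 10, this is 0.04 to 0.2 points. With f = 0.04 it doubles, to 0.08 to 0.4. Equal shares and equal differences in both arms cancel.

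The documents give no HIT-6 effect or SD, so power for HIT-6 cannot be recomputed.

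**The case against.** The case for leaving the set alone is reasonable. One valid month of three is enough for entry. Patients had to complete 24 of 28 screening days, compliance is checked every 4 weeks, and those who withdraw are expected to keep the diary until the Withdrawal Visit unless they withdraw consent. Losing a Week 12 HIT-6 score therefore takes a patient who fails the diary in all three months, falls outside the weighting rule and still completes the questionnaire. A single efficacy set keeps denominators consistent. Classification for the Placebo-controlled Period is done before unblinding, and APTS and FAS counts are reported by arm. The scales other than HIT-6 are outside the testing strategy and carry nominal p-values.

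Most of this stands as a limit on size. It does not remove the inconsistency. Blinded classification does not restore the scores, and the APTS and FAS counts do not show how many excluded patients had HIT-6 data.

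A reader might go further and infer that the plan discards the very withdrawals its HIT-6 estimand names, those for lack of efficacy or adverse events. The documents do not support that: weighting keeps most of them, leaving only cases (c) and (d) exposed. Nor do the documents show that the dropped patients did worse than the rest.

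**Conclusion.** The point holds as a small, avoidable mismatch between the analysis set and the HIT-6 estimand. It is clearest for group (b), where a Withdrawal Visit score is assigned to Week 12, should be used under the inherited treatment-policy strategy, and is then excluded. Group (a) is selection on diary behaviour. Groups (c) and (d) arise from gaps in the weighting rule.

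The expected effect is minor: at most about 17 of 840 patients, about 1% in standard error, and 0.04 to 0.2 points in the one-arm scenario, against the 5-point reduction that the SAP uses for HIT-6 response. These figures rest on the plan's 2%, which is a planning assumption and not a ceiling, and on assumed differences of 2 to 10 points. No conclusion in Steps 5 or 6 is shown to be at risk. The reason to act is that the correction costs little and aligns the analysis with the stated estimand.

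**What to change.** For HIT-6 (main analysis and placebo-based imputation) and the other scale endpoints, use all APTS patients with a baseline value, where the scale has one, and at least one post-baseline value of that scale in the Placebo-controlled Period. PGIC and MBS have no baseline score, so for them a post-baseline value suffices. Keep the FAS for diary endpoints, and align Protocol 16.2 with the new wording.

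The protocol's list of changes indicates that sponsor personnel involved in reviewing the study report were unblinded after the database lock for the Placebo-controlled Period. If the data are already unblinded, leave the planned analysis in place, add this one as a labelled supplementary analysis, and report by arm how many HIT-6 scores the FAS excludes.

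No new data are needed. The cost is SAP and protocol wording, and slightly different patient numbers in the diary and questionnaire tables.
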